Accordingly, in this proposed study, we will determine if an individually tailored diet and PA enhancement program (TDPA), as compared to standard care controls (SC), can improve mobility (six minute walk, 6MW), physical activity (PA), and neuropathy measured using the IENFD. To our knowledge, no randomized controlled intervention trial has been directed toward actually reducing the progression of peripheral neuropathy, as well as determining the effect of this reduction on key factors such as mobility function and PA. The study will be performed at two sites – the Baltimore VAMC/University of Maryland and the Ann Arbor VAMC/University of Michigan and will leverage the strengths of both institutions (senior VA investigators and GRECC Directors at both sites) to increase the diversity and size of the participant recruitment sources and resources available to the study.

While other interventions, for example glucose-regulating medications, may affect mobility and neuropathy progression in patients with IGT, these approaches are costly and fail to address intrinsic problems in the patient's lifestyle. At present we do not know if a lifestyle intervention as proposed in this study will be effective, because such an intervention has never been tested in a randomized study. This is a fundamental question that needs to be answered. In this study we will use a home-based program that can be used within the community and therefore can be used by the majority of patients with IGR.

This study is novel and timely in that it will: 1) test the efficacy of a TDPA protocol in preventing the progression of neuropathy and improving mobility function and PA in participants with IGR; and 2) explore if these processes are associated with changes in metabolic state of the trial participant.

(2) Endpoints and Hypotheses

Endpoints and hypotheses are prioritized according to their importance in the present proposal as the key endpoints (primary and then secondary) and those of lesser importance (tertiary and exploratory/mechanistic).

Endpoints

6 month

12 month

Primary	6 minute walk (6MW)	
Secondary	Physical activity (PA)	IENFD
Tertiary		6MW, PA

Primary Hypothesis (6MW at 6 months): Compared to IGR participants advised to follow the current standard care recommendations on diet and PA (Standard Care or “SC”), IGR participants undergoing TDPA enhancement program will show greater improvement in the 6 Minute Walk (6MW) at 6 months.

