Fig. 2. Change in weight with diet and exercise is dependent on the intensity of the protocol. Subjects in the placebo arm of the DPP study

contrast, the DPP lifestyle group and FDPS had a more intense diet and exercise protocol and a greater mean % weight loss. IGTN subjects where the diet and exercise protocol were less intensely monitored than the DPP "lifestyle group", but more than the DPP "placebo" group, fall between these two groups.

[figure not shown]
Improvement in metabolic control with diet and exercise is associated with improvement in clinical, electrophysiological, and pathological measures of neuropathy. The improvements in metabolic function were associated with a trend toward improvement in neuropathy (Fig. 3-right). The greatest improvement was in the IENFD and QSART, measures of small nerve fiber function, whereas there was less change in NCS and other measures of large nerve fiber function. This supports the concept that small fibers are the first to recover in IGT associated neuropathy and that it may

take longer than 1 year for large fiber function to change. Small fiber and sensory subscores of the MDNS show the same change. In Fig. 3, changes on the right indicate improvement and left worsening. * = p<0.05. IENFD was measured from 3-mm skin biopsies at the distal leg and proximal thigh at baseline and after 1 year in subjects with IGT (See Appendix). Each received diet and exercise counseling as a standard of care. NCS, QSART, and the MDNS were performed, and a visual analog pain scale was completed. Baseline distal IENFD was 0.9+1.2 fibers/mm and proximal IENFD was 4.8+2.3 fibers/mm. Baseline distal IENFD correlated with fasting glucose (0.001) and OGTT (0.01). After 1 year of treatment, there was a 0.3+1.1-fiber/mm (30%) improvement in distal IENFD and a 1.4+2.3-fiber/mm (70%) improvement in proximal IENFD (0.004). There was a greater improvement in the proximal thigh because many participants had no distal skin fibers, but all had proximal fibers, thus proximal IENFD may be a better measure of early nerve regeneration. Proximal IENFD was used to power the IENFD endpoint in the current proposal. The change in proximal IENFD correlated with a change in sural sensory amplitude (0.03).

This data represents a mean of the whole natural history cohort and cannot separate out those participants who showed the greatest improvement in weight loss and exercise capacity. The current proposal will address this question.

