Sample size will be based on the previous data from our IGTN natural history study and relevant pilot data from our ongoing Rehab R&D-funded Merit Review T2DM exercise study. An assumption is that the IGTN study represents a more intense intervention than SC and that the difference between the TDPA and the SC will be at least as large as the difference between baseline and the 6 or 12 months endpoints of IGTN (see below). The table below uses the IGTN baseline-endpoint data to compute an adjusted standard deviation (i.e. the SD can be reduced by taking into account the contribution of each individual's baseline in explaining the overall variation). For the T2DM study, PA (from CHAMPS scores) is available at baseline (Mean \pm SD 1350.5 \pm 946.5) and at 10 weeks of a physical activity enhancement intervention for our pilot group (10 week delta=over 600). At present, we do not have sufficient 6 or 12 month data for PA in T2DM, but we anticipate that the initial PA benefit may be sustained. The expected sample size required is noted for two-sided alpha=0.05 and with power of 80%.

Study	Variable	SD of the outcome adjusted for baseline	Desired TDPA-SC difference	Effect size for adjusted outcome	Sample size per group
IGTN	6MW	97	50	0.51	64
IGTN	IENFD	2.2	1.0	0.45	53
T2DM	PA	1000	500	0.50	64

Thus, the sample size estimate needed for the primary hypothesis efficacy measure (6MW) will be 64 per group for a total of 128 needed in the study. In the T2DM CHAMPS PA data, using baseline information and assuming a delta of 500 and standard deviation of 1000, with 64 subjects per group we can detect an effect size of 0.5. Based on reliable data from the current IGTN study, we know that the actual 1 year dropout for enrolled subjects is 4%, so that the number of subjects to be enrolled is 133. We estimate a more liberal 10% dropout rate from

baseline to the 12 month endpoint, thereby requiring randomization at baseline of 142 in order to guarantee recruiting the necessary 128 participants.

The sample size estimate needed for the secondary hypothesis efficacy measure (IENFD) will be 53 per group for a total of 106 needed in the study. Using the 10% dropout rate from baseline to the 12 month endpoint, 117 would be required for randomization, well within the 142 planned to satisfy the requirements for 6MW noted above.

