5) Strategies for multiple inferences: The analysis involves several hypotheses tests, thereby requiring a strategy to control the alpha level. We will give higher priority to the primary hypothesis so that the outcomes of tests of mechanism hypotheses will not be given the same strength of interpretation. Overall significance levels will be controlled using the probabilistic inequalities (e.g. Bonferroni or Sidak's methods), adjusted confidence limits (e.g. Tukey), methods based on resampling (109) or other appropriate multiple comparison adjustment methods (7).

Hypothesis testing plan

For the purposes of hypothesis testing, specific key primary and secondary variables, based on previous pilot data have been identified.

Endpoints	6 month	12 month
Primary	6 minute walk (6MW)	
Secondary	Physical activity (PA)	IENFD
Tertiary		6MW, PA

Primary Hypothesis (6MW at 6 months): Compared to IGR participants advised to follow the current standard care recommendations on diet and PA (Standard Care or "SC"), IGR participants undergoing TDPA enhancement program will show greater improvement in the 6 Minute Walk (6MW) at 6 months.

Secondary Hypothesis 1 (PA at 6 months): At 6 months and compared to SC, TDPA participants will show greater improvement in self-reported PA.

For the Primary Hypothesis and Secondary hypothesis 1 that address the 6-month 6MW and PA intervention effect, the goal is to determine whether there is a group (TDPA versus SC) difference in 6-month improvement. A regression model will be used to test these hypotheses

controlling for the minimization variables and baseline outcomes (BA=outcome at baseline; GEN=Gender; BMI=Body Mass Index, Age=Age, GRP=intervention group):
Outcome at 6 months= BA+GEN+BMI+AGE+GRP

Secondary Hypothesis 2 (IEFND at 12 months): At 12 months and compared to SC, TDPA participants will show better maintenance of IEFND.

A similar strategy will be used to test for the 12 month intervention effect.

Outcome at 12 months= BA+GEN+BMI+AGE+GRP

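### The IENFD sample size does not give the stated 80% power on its own inputs; PA power has no slack if alpha is adjusted, and the PA endpoint is not fixed

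*Combined protocol and SAP*

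**What the plan says.** Endpoints and Hypotheses sets a ranking: "Endpoints and hypotheses are prioritized according to their importance in the present proposal as the key endpoints (primary and then secondary"). The six-minute walk (6MW) at 6 months is the single primary. PA at 6 months and IENFD at 12 months are the secondaries.

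Sample size calculation puts all three in one table: "The expected sample size required is noted for two-sided alpha=0.05 and with power of 80" percent. The rows are:
- 6MW: SD 97, difference 50, 64 per group.
- IENFD: SD 2.2, difference 1.0, effect size 0.45, 53 per group.
- PA: SD 1000, difference 500, effect size 0.50, 64 per group.

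The text repeats the IENFD figure, "The sample size estimate needed for the secondary hypothesis efficacy measure (IENFD) will be 53 per group", and concludes that "117 would be required for randomization, well within the 142 planned to satisfy the requirements for 6MW".

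General analytic plan, item 5 (Strategies for multiple inferences), says that several tests require alpha control: "Overall significance levels will be controlled using the probabilistic inequalities (e.g. Bonferroni or" Sidak), or Tukey limits, resampling or other methods. It gives the primary priority over the mechanism tests. It fixes neither the method nor the set of tests it covers.

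The PA endpoint varies by section:
- Secondary Hypothesis 1 under Endpoints and Hypotheses adds Actigraph-measured exercise to self-report.
- Specific Aim 1, the Hypothesis testing plan and Table 5 use self-report (CHAMPS) only.
- Self report measures analyses two CHAMPS scores.
- Measured physical activity makes the Actigraph a check on CHAMPS.
- Sample size calculation says only that "PA (from CHAMPS scores) is available at baseline", without saying which score.

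**The concern.** Within one table, at one alpha and one power, the smallest effect size (0.45) is given the smallest sample (53), while 0.50 and 0.51 are given 64. A smaller effect needs more participants, so one figure must be wrong.

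IENFD is the trial's neuropathy endpoint. A null result would be read as the outcome of an 80%-powered comparison, when the plan's inputs give a miss rate of about 28% at 64 per group, not 20%.

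Two open choices add to this. The table uses an unadjusted alpha while item 5 promises control, so the power that applies to PA and IENFD is not known. And if the PA variable or the multiplicity method is picked after unblinding, a positive claim would be open to the charge of selection.

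**Working it through.** **Method.** Two-sample comparison, 1:1, two-sided. Normal approximation: n per group = 2(z₁₋α/₂ + z₀.₈₀)²/d² = 2(1.960 + 0.842)²/d² ≈ 15.70/d² at alpha 0.05. Power ≈ Φ(d√(n/2) − z₁₋α/₂). Final figures use the exact noncentral t.

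**Reproducing the plan's other figures.**
- PA: d = 500/1000 = 0.50; 15.70/0.25 = 62.8, so 63 (t: 64). The stated 64 reproduces.
- 6MW: d = 50/97 = 0.515; 15.70/0.266 ≈ 59.1, so 60 (t: 61). The stated 64 is close, and gives 82% power.
- Dropout: 128/0.90 = 142.2 and 106/0.90 = 117.8, matching 142 and 117.

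**IENFD.** d = 1.0/2.2 = 0.4545; 15.70/0.2066 ≈ 76, and the t calculation gives 77. One-sided 0.05 gives 60 to 61, and 70% power gives 60. Neither yields 53. A t-test with d = 0.55 does give 53, which would fit a slip from 0.45, but that is only an inference.

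| n per group | d√(n/2) | Power, normal | Power, t |
|---|---|---|---|
| 53 (stated) | 2.340 | 65% | 64% |
| 64 (planned completers) | 2.571 | 73% | 72% |
| 71 (all 142 evaluable) | 2.708 | 77% | 77% |

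To randomise for 77 per group: 154/0.90 = 171.1, about 171, which exceeds 142. At 64 per group and SD 2.2, 80% power needs a difference of about 1.1.

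**PA and IENFD if alpha is adjusted (64 per group).**
- At 0.05, PA: Φ(2.828 − 1.960) = 81% (t: 80%).
- At 0.025, PA: Φ(2.828 − 2.241) = 72% (t: 71%). IENFD: Φ(2.571 − 2.241) = 63% (t: 62%).
- Holm over the two secondaries, by simulation with assumed test correlation 0 to 0.5: PA about 76–78%.
- With 4% dropout, the rate reported from the natural history study, 142 × 0.96 = 136.3, or about 68 per group. Holm then gives PA about 79–80%.
- Holm only after a significant 6MW, 64 per group, same correlations: PA about 63–68%, IENFD about 57–63%.

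**Overall error.** If 6MW is tested at 0.05 and Holm is applied to the secondaries with no gate, the chance of at least one false finding in favour of TDPA, with no effect on any of the three, is 4.3–4.9% (correlation 0.5 to 0), against a nominal 2.5%. The gate removes this excess.

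**The case against.** **PA.** The 64 per group is right at the alpha stated. Item 5 fixes no method; Tukey, which it lists, changes nothing with two groups; and a fixed sequence would leave PA's own test at 0.05. With 4% dropout, Holm gives about 79–80%. All of this stands. A reader might infer that PA is underpowered as planned, but the documents support only a conditional statement.

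**IENFD.** Enrolment is set by 6MW, so nobody plans to stop at 53, and at 64 per group the detectable difference moves only from 1.0 to about 1.1. That is fair. The plan also argues that its inputs are conservative, since it expects a between-group difference at least as large as the natural history study's change, reported as "1.4+2.3-fiber/mm (70%) improvement in proximal IENFD". A difference of 1.4 would give 91% even at 0.025 and 64 per group with SD 2.2, or 88% with SD 2.3. Similarly, the PA pilot change ("10 week delta=over 600") taken as 600 would give 87% at 0.025. Both are uncontrolled before-after changes, and the sponsor planned on 1.0 and 500. They are range checks and do not make the IENFD row correct.

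Covariate adjustment is no ready rescue. The SD is already adjusted for baseline. Reaching 80% at 64 per group needs d of about 0.499, so SD about 2.00, and 1 − (2.00/2.2)² ≈ 17% of residual variance explained by age, gender and BMI. The IENFD description says age and gender do not affect the change.

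**Stronger readings.** A reader might take the Actigraph wording to mean that both PA measures must succeed, or take the several measures to mean that any one suffices. The plan states neither rule, so no power or error figure should be attached to either. A reader might also infer that the primary is underpowered. The endpoint ranking supports testing 6MW first at the full 0.05, though item 5 does not say so in terms.

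**Conclusion.** The IENFD statement is wrong as written. It needs no multiplicity assumption, only the row's own SD, difference, alpha and power: 77 per group rather than 53, about 171 randomised rather than 117, and 72% power at the planned 64. The claim that the requirement fits inside 142 fails.

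The PA shortfall is conditional. It arises only if the chosen method lowers PA's alpha or makes its test depend on 6MW, and its size depends on that method, on dropout and on the assumed correlation between tests.

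The conflict between sections over what Secondary Hypothesis 1 measures is confirmed by the text. It is an unreconciled definition, not evidence of a particular success rule. The primary analysis and the enrolment target are unaffected.

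**What to change.** 1. **Sample size calculation.** Replace 53, 106 and 117 in the IENFD statement with figures that follow from 1.0/2.2, remove the claim that these fit inside 142, and state IENFD power at 64 per group (about 72% unadjusted). Do not add enrolment. Restate PA and IENFD power at the alpha actually used.
2. **Multiple inferences (item 5).** State that 6MW at 6 months is tested first at two-sided 0.05 with the 6-month regression model in the Hypothesis testing plan. This needs saying because the same section later names the overall repeated-measures effect as the main interest. Name one method that controls overall error, for example Holm over PA and IENFD only after 6MW is significant. If the sponsor prefers no gate, label the secondaries as not controlled for overall error.
3. **PA endpoint.** Before unblinding, name one variable for Secondary Hypothesis 1 (the CHAMPS score that was powered, if CHAMPS is kept). Treat the other CHAMPS score and the Actigraph comparison as supportive. Reconcile Secondary Hypothesis 1 in both places, Self report measures, Measured physical activity and Table 5.

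The cost is wording only, with no added participants or measurements; both arms already wear the Actigraph at all three timepoints. The price is less favourable stated power for the secondaries, and gating lowers it further, to the ranges shown in the working.

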Choice of biopsy site is important. While 24% of subjects in the IGTN study had absent epidermal nerve fibers distally, all had preserved fibers at the proximal site, making it possible to measure a change in IENFD in each subject. Once there is loss of the dermal plexus, the likelihood of epidermal reinnervation is remote. IGTN subjects with absent distal IENFD did not improve at 1 year if there was loss of the dermal plexus as well (see Work Accomplished). While biopsy of the distal site provided useful correlative data with other neuropathy measures, it was less useful in measuring improvement. In the IGTN study, as in other studies, the biopsy

procedure was well tolerated without significant side effects, and patient compliance with repeat biopsy was high (29;31). In conclusion, IENFD is a sensitive and valid surrogate measure of the mixed, but predominantly small fiber, neuropathy typical of IGTN.

In this study, in addition to the IENFD, a clinical measure of neuropathy severity, the MDNS will also be used to monitor neuropathy progression. The MDNS and NCS have been used in most studies of diabetic neuropathy outcome. Both these measures have been well validated in numerous studies including the Epidemiology of Diabetes and Complications Trial (EDIC) and IGTN study (MDNS) and the EDIC, IGTN and Rochester Diabetic Neuropathy Study (NCS) (18;33-36). In the recent IGTN study, there was at least 1 abnormality of the NCS in nearly 60% of participants, and while they are not as sensitive as the IENFD, NCS performed better than quantitative sensory testing which will no longer be performed. Although the MDNS and NCS are not as sensitive as the IENFD in diagnosis of early neuropathy and would require a much larger study if used as primary or secondary endpoints, they are still very well-validated measures and for this reason will be used in this study to monitor neuropathy progression.

T2DM and functional mobility impairment

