participant every 6 months and could contact them by telephone or email every 3 months depending on the participant's needs. The study enrolled 67 subjects, 61% were women and the mean age was 57 (range 38-75 years). In general, baseline characteristics of this cohort reflect typical features of the metabolic syndrome. The average body mass index (BMI) is 32.7 (obesity is defined as BMI > 30). Prior to enrollment, participants were inactive, reporting an average of just 12 minutes of recreational exercise weekly, however after enrollment they were able to comply with the diet and exercise protocol (Fig 1) although most of the improvement in weight occurred within the first 6-12 months (Fig. 2). In the IGTN study, the diet and exercise advice was given to all participants as standard care, was not intended as a specific intervention, and did not include a balance component. Thus, the IGTN study failed to answer certain critical questions that a comparison intervention study will help to clarify. **At the end of the current proposal we should be able to determine if an intensive home-based diet and exercise program can improve walking and PA, and reverse neuropathy in subjects with IGR. The study will also determine if there is a rational and sustained metabolic basis for this improvement in neuropathy and functional state. The main outcome variables will be 1) the 6MW, 2) the IENFD, and 3) PA.**

The preliminary data presented in Work Accomplished support the concept that somatic and autonomic neuropathy in participants with IGT may improve concurrent with the improved metabolic control associated with diet and exercise. The current proposal will use the expertise gained from the IGTN study to examine the TDPA intervention.

Fig. 1. IGTN subjects have complied with the diet and exercise program. Subjects were asked to lose 7% body weight and increase weekly exercise to 150 minutes per week. The graphs show the percent of participants meeting each goal level.

The DPP and Finnish Diabetes Prevention Study (FDPS) provide benchmarks for compliance with individualized diet and exercise regimens in subjects with IGT. These studies

[figure not shown]
used intensive counseling schedules to motivate compliance. Although these intensive intervention studies resulted in rapid weight reduction, most of the reduction occurred within the first 12 months, thus

supporting the duration of the current proposal.

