Description: Subject begins test standing one meter behind the line. Subject performs the test in usual footwear and may use a walking aid if so desired. A practice trial is performed, followed by a timed trial. Examiner walks to the side and slightly behind the participant, being careful not to pace the subject.

Instructions to subject: "This is our walking course. When I say 'go,' I would like you to walk to the other end of the course at your usual speed, just as if you were walking down the street."

Walk past the tape at the other end before you stop. I will walk with you. If you use a cane or other walking aid and would feel more comfortable with it, you may use it.”

Scoring: Timing begins as the subject walks across the first line and ends when the participant’s toe crosses the end line. Note whether an assistive device is utilized to perform the task.

Self report measures

- 1) Self-reported PA (CHAMPS): PA will be measured by the CHAMPS questionnaire, which was specifically designed for use in evaluating intervention-induced changes in a broad range of self-selected physical activities, similar to that proposed in the present study (95). This questionnaire was validated using an intervention to improve self-selected physical activities, in a group of older adult participants (mean age 76) with significant health problems (54), and in diverse populations older than age 40 years (96). Two measures will be used in the analyses, first, calories expended for all activities and then calories expended performing activities of moderate intensity or greater, the latter a measure of more aerobically challenging activity. Furthermore, PA compliance will be confirmed using a actigraph measurement
- 2) Neuropathy Specific Quality of Life Instrument (NeuroQoL) and SF12: The NeuroQoL is a recently introduced patient-specific, neuropathy-centered instrument to evaluate quality of life in participants with diabetic neuropathy (97) and consists of 6 domains consisting of 43 items with subscores and a total weighted score. The NeuroQoL will be used to monitor changes in quality of life between the SC and TDPA groups. The SF12 is a short form version of the SF36 and shows a high degree of correlation with the SF36 used widely as a QOL measure.
- 3) Subject and examiner indication of the subjects group assignment. Both the subject and the examiner will indicate whether they think the subject is in the TDPA or the SC group

Measured physical activity

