This study will use a lifestyle intervention and it is not predicted from the current IGTN study that a standing independent SDMC will be required. If necessary, a plan for convening a SDMC is described in Human Studies (see Appendix).

General analytic plan

Comparability of treatment groups will be performed using the baseline demographic variables (i.e. age, gender, BMI) and relevant prognostic covariants (e.g., HbA1c, autonomic symptoms, and baseline values of primary endpoints). The demographic and prognostic values will be presented by treatment group as means and standard deviations for continuous variables, and analysis of variance will be used to compare the means of the two treatment groups, controlling for baseline. Baseline characteristics will be compared between the study groups. Standard two group comparison methods will be used, such as two sample t-tests for normally distributed variables. Measures of central tendency (means) and variability (standard deviations, ranges) will be estimated. Initial data analyses will allow us to explore the distributions of outcomes studied, may lead to transformation of the dependent variable, and may help identify outlying measures not detected earlier in the data cleaning process.

1) Model check and alternative analysis plans: Model fits will be checked for individual and systematic departures of the observed and fitted values using informal (e.g. inspection of residuals) and formal methods (e.g. based on score tests for extra parameters (104;105). The influence of individual outliers will be evaluated by comparing models with and without outlying values. Outcome variables will be transformed when we cannot fit a parametric model. In our

preliminary data, assumption of normality is reasonable for most outcome variables, including those which are log transformed. Non-parametric analyses e.g. Generalized Additive Models (GAM), (106), or Friedman two-way analysis of variance (105), will be utilized when we cannot fit a parametric model. Outcome measures will be adjusted for baseline by including baseline values as a covariate into the model. As another option, a baseline measure becomes another dependent variable in the repeated measures model and appropriate contrasts will be constructed to adjust for baseline. In computations, SAS PROC MIXED (107), SAS PROC GENMOD, and PROC GAM in SPLUS will be used.

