The key parameter tested in all of these models is the group variable (GRP). The training efficacy hypotheses will be tested by comparing two nested models with and without GRP. The outcome at baseline and gender, BMI and Age variables are included to adjust the primary outcome for its baseline value. Assuming that residuals from the model fit are normally distributed, the analysis is equivalent to a classical analysis of covariance. For outcomes that do not fit a normal distribution, inverse, logarithmic or power transformations will be performed or generalized linear models (GLM) (110) with Poisson or gamma error will be considered. Since the outcomes are measured on three occasions (baseline, 6 months and 12 months), a model that takes into account repeated measures will be developed in the framework of linear mixed effects models (LME) or generalized linear mixed effects models (GLMM). Models for repeated measures will yield three tests: 1) a test for outcome changes over time of the study (time effect); 2) a test of group differences (an intervention effect); and 3) a test for interaction of intervention effect with time. We are primarily interested in the overall intervention effect. However, a changing intervention effect over time as reflected in an intervention by time interaction is of great interest since it might suggest that the intervention has a greater impact as time progresses.

Additional data analyses

A number of additional key variables will be assessed in order to investigate the maintenance of PA and 6MW improvement and mechanisms underlying the changes in neuropathy progression and mobility function.

Tertiary hypothesis (Maintenance of 6MW and PA at 12 months): At 12 months compared to 6 months, and compared to SC, TDPA participants will show greater sustained improvement in 6MW and self-reported PA.

Exploratory/mechanistic hypothesis: Improvement in measures of neuropathy (NCS, MDNS, IENFD), mobility function and PA will correlate strongly with each other and with improvement in specific measures of metabolic function and weight loss

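### Poisson error is listed as a fallback for non-normal endpoints; on CHAMPS calories, with dispersion fixed at 1, it would reject in about 90% or more of null trials

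*Combined protocol and SAP*

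**What the plan says.** The Hypothesis testing plan (section C(1)) regresses each endpoint on its baseline value, gender, BMI, age and group. Group is tested by fitting the model with and without that term. For outcomes that are not normal, "inverse, logarithmic or power transformations will be performed or generalized linear models (GLM) (110) with Poisson or gamma error will be considered". No option is tied to an endpoint, and no link, dispersion scale, robust variance or rule for zeros is given.

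The General analytic plan (item 1, model check) adds that "Outcome variables will be transformed when we cannot fit a parametric model", names generalized additive models and the Friedman test as further alternatives, and calls for residual inspection and formal score tests. It does not say whether these choices are made without knowledge of group.

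Under Self report measures, PA is analysed as CHAMPS calories for all activities and as "calories expended performing activities of moderate intensity or greater". In the Sample size calculation, "PA (from CHAMPS scores) is available at baseline", with mean 1350.5 and SD 946.5 from the type 2 diabetes pilot.

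**The concern.** Poisson error forces the variance to equal the mean. That can suit event counts. It does not suit calories (PA), a distance (6MW) or a fiber density (IENFD). If the real variance is far larger, the standard error of the group effect is far too small, and a trial with no effect will usually look positive. PA at 6 months is Secondary Hypothesis 1, so a claim of efficacy could rest on this.

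A smaller matter is zeros. The log, the inverse and the gamma likelihood are undefined at zero, and the plan does not say what happens to participants with zero values.

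The scale is also to be chosen after the outcome distributions are explored, and the plan does not state that this is done without the group term.

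**Working it through.** **The plan's own figure.** For PA, with difference 500, SD 1000, two-sided 0.05 and 80% power: n = 2 × (1.960 + 0.842)² × (1000/500)² = 62.8, so 63 per group; the t-test version gives 64. The stated 64 per group reproduces. It rests on a difference in untransformed units.

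**Dispersion.** φ = SD²/mean = 946.5²/1350.5 = 663. The true standard error is √663 ≈ 26 times the Poisson one.

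**Null rejection rate with dispersion fixed at 1.** The rate is P(|Z| > 1.96/√φ). Here 1.96/25.8 = 0.076, which gives 93.9%. With the planning SD of 1000, φ = 740 and the rate is 94.3%.

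**Allowing for baseline.** With baseline correlation r, φ becomes 663 × (1 − r²). The documents do not give r, so a range is shown. The planned model was also simulated: 64 per group, gamma-shaped values with the stated mean and SD, no group effect, and 1,000 trials for each r (correlation set on a latent normal scale). For the Poisson model with dispersion 1, group was tested by nested deviance.

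| r | φ | Formula, dispersion 1 | Simulated, dispersion 1 | Poisson, Pearson-scaled | Poisson, robust (HC1) | Gamma, log link | ANCOVA |
|---|---|---|---|---|---|---|---|
| 0 | 663 | 93.9% | 93.0% | 5.2% | 6.0% | 6.0% | 4.9% |
| 0.5 | 498 | 93.0% | 92.8% | 4.9% | 5.6% | 5.6% | 4.1% |
| 0.7 | 338 | 91.5% | 92.2% | 5.2% | 5.4% | 4.9% | 4.1% |
| 0.8 | 239 | 89.9% | 90.8% | 6.0% | 5.9% | 5.2% | 4.6% |
| 0.9 | 126 | 86.1% | not run | not run | not run | not run | not run |

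The simulation standard error at 5% is √(0.05 × 0.95/1000) = 0.7 percentage points, so the last four columns are all close to nominal.

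**Unit dependence.** Dividing every value by 100 gives mean 13.505 and SD 9.465, so φ = 6.6 and the rate is about 45%. A valid test would not change with the unit.

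**Robust errors for ANCOVA.** In a separate null simulation of 600 trials with correlation about 0.5, ANCOVA rejected in 3.8% with ordinary and 3.7% with HC3 standard errors. HC3 shows no gain here.

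**Zeros.** At zero, log and inverse are infinite and the gamma log-likelihood is not finite; a square root is defined. The section on endpoint measures of neuropathy says that "24% of subjects in the IGTN study had absent epidermal nerve fibers distally", but the same sentence says that all had fibers proximally, and section B says that the proximal site was used for power. Both thigh and calf are biopsied, and the Hypothesis testing plan does not name the site tested. For moderate-intensity calories, zeros are plausible because the IGTN cohort was "reporting an average of just 12 minutes of recreational exercise weekly" before enrollment, but no count of zeros is reported. None is reported for 6MW or total calories either.

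**The case against.** The best defense is that Poisson is one of several options and is only to be considered. The General analytic plan requires residual and score-test checks, and a 663-fold excess of variance would be hard to miss. That section also reports that normality was reasonable for most outcomes in preliminary data, some after a log transformation, so ANCOVA or a log scale is the likelier route. An analyst could also use scaled or robust variance, which brings the rate back to about 5% to 6%. The plan mentions mixed models too, and whether participant random effects would absorb some of the excess was not calculated. All of this stands, and it limits the point to a listed option rather than the expected analysis. It does not justify keeping the option: the plan specifies neither scaling nor robust variance, and states no consequence if the checks show overdispersion.

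A reader might infer more than the documents support:

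- **That none of the fallbacks suits these endpoints.** Power transformations are in the same list and can take zeros, and the gamma model held 4.9% to 6.0% on positive data.
- **That a quarter of participants would break the IENFD analysis.** The 24% is at the distal site; the site used for power had no zeros.
- **That the primary endpoint is compromised.** The mean 6MW is not given. With SD 97, assumed means of 350 to 1500 give rates from 71% down to 43%, but nothing suggests that 6MW would fail the normality check or be modelled as Poisson.
- **That PA's spread will trigger the rule.** A coefficient of variation of 946.5/1350.5 = 0.70 describes raw baseline values; the normality assumption concerns residuals after adjustment.
- **That the statistician who issues allocations also picks the model.** The documents do not say who makes that choice, or whether that person is unblinded.

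**Conclusion.** The point holds for Poisson error on CHAMPS calories. With dispersion fixed at 1, the false-positive rate is about 90% to 94% for baseline correlations up to 0.8 and about 86% at 0.9. This assumes that the pilot mean and SD are in the calorie units to be analysed (the Sample size calculation states no unit), that the 6-month distribution is similar, and, for the simulated figures, a gamma shape. It is not a forecast of the trial's error rate, because the plan does not commit to Poisson.

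The zero problem is conditional: it matters if distal IENFD is analysed and, plausibly, for moderate-intensity calories. Harm to 6MW is not shown. The wording should be changed before analysis because an invalid option is open for a named secondary hypothesis and nothing requires the scale to be chosen without the group term.

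**What to change.** 1. In the Hypothesis testing plan, delete Poisson error for 6MW, PA and IENFD, or require Pearson-scaled or robust variance wherever it is used.
2. Keep the stated ANCOVA on the measured scale as the test of group for each endpoint, which also matches the scale of the powered difference. Robust standard errors can be optional.
3. Make transformed and gamma models sensitivity analyses, using forms that retain participants with zero values. Name the IENFD site so that it is clear whether zeros arise there.
4. Do distribution and outlier checks on pooled residuals from the model without the group term, before allocation is merged.
5. Apply the same rules to the generalized additive and Friedman alternatives in the General analytic plan.

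This is a change of wording only. The downside is some loss of efficiency against a log scale if an outcome proves strongly skewed. Items 1 and 4 matter most; making the measured scale the fixed choice is partly a matter of preference.
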